Study Protocol

Evaluating Two Types of Cognitive Training in Veterans with Schizophrenia

NCT 01891721

11/24/14

Background and Significance

One of the most exciting developments in the treatment of schizophrenia in the past decade has been the rise of cognitive remediation (CR). CR is a “behavioral training based intervention that aims to improve cognitive processes (attention, memory, executive function, social cognition, or metacognition) with the goal of durability and generalization” [1]. This collection of interventions aims to restore cognitive functioning by targeting different levels of cognition from basic perceptual processes (e.g., auditory or visual processing) to the more molar and complex cognitive skills (e.g., memory, problem solving). CR has been used in disorders other than schizophrenia, such as stroke, TBI, PTSD, and ADHD. Yet, its popularity in schizophrenia has grown because cognitive impairments are a core feature of the illness and remain unsuccessfully treated with the available antipsychotic medications. Schizophrenia is a disorder that affects both higher-level neurocognitive operations and lower-level perceptual processes. These deficits contribute to the poor community outcome and high levels of functional disability seen in patients [2]. Therefore, treatment of the cognitive dysfunction associated with this illness is important to achieve improvements in daily functioning. Numerous evidence-based approaches to CR have been developed to treat the cognitive deficits in schizophrenia. In general, improvements in cognition have been found with both cognition-enhancing approaches that attempt to restore neuronal and neurocognitive functioning, as well as compensatory approaches that seek to circumvent cognitive impairments to improve broader aspects of function [3]. Recent meta-analytic studies on cognitive training in schizophrenia [4, 5] report that cognitive training has a moderate effect-size impact on cognitive functioning (0.45) and a lower impact on daily functioning (0.36) and clinical symptomatology (0.28). Based on these studies, 2104 inpatients and outpatients with schizophrenia (with a mean age of 36 years old and a high school education) have participated in randomized controlled trials (RCTs) of cognitive interventions. They were typically exposed to 17 weeks of treatment, receiving about 32 hours at a dosage of 2 to 3 times a week. The interventions in these RCTs consisted of drill-and-practice training, as well as strategy-based learning.

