This proposal will determine which training approach leads to the largest magnitude of improvement in neurocognition, functional capacity, and neural functioning measured with EEG. Moreover, it will shed light on the underlying mechanism of action associated with the observed improvements in cognition. Based on the neuroscience-guided theoretical framework described above, we expect that the effects of the bottom-up training 1) will result in robust changes in higher-order cognitive operations, 2) will be evident at the earliest stages of auditory processing (normalization of MMN), and 3) will generalize to functional capacity. We also expect that the bottom-up training will lead to superior effects on the primary and secondary outcomes relative to the top-down training. The proposed study will help to decide how best to implement CR interventions to improve the cognitive and social functioning of patients with schizophrenia. Subsequent studies could consider additional research questions, such as whether the benefits of training are maintained over time. Depending on the results of this study, treatment providers at the VAGLAHS will be able to decide which version of CR will lead to more substantial gains. Our prediction is that it will be the neuroplasticity-based intervention. However, this study will provide a clinically meaningful answer, even if our hypothesis is incorrect.

Preliminary Studies

Previous Work on Neurocognition in Schizophrenia

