
Randomization and Treatment Procedure

To optimize power for the primary comparison between the active treatments, we will use a 2:2:1 asymmetrical randomization procedure resulting in a total of 48 subjects in the BFP group, 48 in the Cogpack group, and 24 in the control group. Subjects will be given sequential identification numbers and randomly assigned in blocks of 5 or 10 to maintain balance throughout the study. A random mixture of block lengths will be used to help ensure the integrity of the process and the preservation of the blind. The MIRECC Data Core will create an online randomization system for the project, which will be accessible only to the study coordinator who will perform the assignments. Randomization will be programmed in ASP (Active Server Pages).

Table 1: Enrollment for Each Year

	Year 1	Year 2	Year 3	Year 4
Interviews, BFP, Pre- and Post-Treatment Assessments	12	12	12	12
Interviews, Cogpack, Pre- and Post-Treatment Assessments	12	12	12	12
Interviews, Computer Games, Pre- and Post-Treatment Assessments	6	6	6	6

Patients will be scheduled for training during specific 60-min blocks of time (between 10:00 AM and 2:00 PM) every Monday, Wednesday, and Friday. Treatment will be administered individually in a designated room. However, up to 6 patients may be sharing the treatment room at a time. Each patient will work through different exercises (depending on their assigned treatment condition) on a personal computer station. Patients will be told that they are going to receive training exercises that might or might not improve their cognitive functions. The testers will be blind to the patient's treatment group membership. A staff person will be present in the treatment room and will be aware of the type of training that each patient is receiving, but this person will not administer any outcome measures. They will install the appropriate computer session for each patient and give individualized instruction in the use of the equipment and training program. To ensure maximum compliance, the trainer will provide encouragement, observe patients' behavior throughout the session, and monitor data storage after each session.

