Recruitment will be ongoing and we expect to enroll 30 subjects/year. Based on dropout rates in our previous training intervention studies, we project 20% attrition, which will leave us with an estimate of 96 completers: 38 getting BFP training, 38 getting Cogpack training, and 19 getting the control intervention. We will make every effort to hold patients in the study protocol while emphasizing that their participation is strictly voluntary and that they can withdraw at any time. To minimize attrition, we will inform subjects that they will be in the study up to 17 weeks and ensure that they will not be leaving town or relocating during the study period. We will contact those who opt to discontinue treatment to request that they participate in a final outcome assessment. Details of the plan for handling missing data and minimizing potential threats to randomization caused by differential dropout rates are further described in the data analysis section.

Subjects

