Specific Aim #1: To compare the treatment effects of bottom-up training (BFP) to top-down training (Cogpack) as well as to a control condition on neurocognition.

Specific Aim #2: To compare the treatment effects of bottom-up training (BFP) to top-down training (Cogpack) as well as to a control condition on EEG (MMN).

Specific Aim #3: To compare the treatment effects of bottom-up training (BFP) to top-down training (Cogpack) as well as to a control condition on functional capacity.

Exploratory Aims: 1) To compare the treatment effects of bottom-up training (BFP) to top-down training (Cogpack) as well as to a control condition on social cognition and community functioning and 2) to assess whether changes in MMN are associated with changes in cognition and functioning.

Primary Analyses: To make the most efficient use of our data, our primary analytical technique will be the general linear mixed model (GLMM). GLMMs account for correlations induced by repeated measures within subjects, allow for both fixed and time-varying covariates and automatically handle missing data, producing unbiased parameter estimates provided that observations are missing at random. This allows us to include all available data from all subjects in the analyses, regardless of the degree of study participation or treatment dosage received, consistent with the intent to treat framework. For each of our primary outcomes (MCCB neurocognitive composite for Aim1, MMN amplitude at Fz for Aim 2, UPSA total score for Aim 3), our core model will include group (BFP, Cogpack, control) as the between subject factor, time (baseline, end of treatment) as the within subject factor, and a group by time interaction. Our primary hypotheses correspond to the group by time interactions comparing the outcome trajectories for the two active treatments, which can be obtained as post-hoc contrasts. Such contrasts can also be used to compare each of the active

treatments to the control condition, to test for within group change and to examine the magnitudes of group differences at the end of treatment.

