We plan to enroll 120 subjects (n=48 for each of the two treatment conditions and n=24 for the control group) to obtain a final sample of n=96 subjects with complete data after accounting for attrition and data loss. Power calculations are conservatively based on these numbers and assume a two-sided significance level of $\alpha=.05$. We also assume a within-subject autocorrelation of $r = .7$, a value based on our experience with similar studies in the past. Our primary hypotheses all involve comparisons (parameterized as group by time interactions) among the 3 treatment groups. Our design provides over 80% power to detect overall effects as small as $f=.13$ which is sufficient to detect any pattern of changes in the three study arms for which the difference between the two most extreme groups is at least $d=.6$ at study endpoint. For the post-hoc comparison of primary interest, namely the group by time interaction examining the outcome trajectories for the two active treatment groups, this design provides sufficient power to detect an effect equivalent to a change from no difference at baseline to a difference of $d=.5$ at the post-treatment point. In addition, we note that we have over 80% power to detect within group changes from baseline to end of treatment of $d = .35$ in the active treatment groups and $d = .5$ in the control group, small to medium effects using the conventions of Cohen. For the exploratory analyses, the relationships will be assessed using the entire sample. This yields 80% power to detect a correlation of $r = .28$ between measures at any time point; power for the model with time-varying covariates will be higher due to the repeated measures.

In our pilot data, which examined performance on Cogpack training tasks in patients receiving two sessions per week over a 1 month period, we observed within group changes ranging from $d = .5$ (connect task) to $d = 2.5$ (confusion task). While these effect sizes cannot be used directly to compute power for our primary hypotheses (since they involve different measures and only a single group) they do show that patients can experience large cognitive changes over a much shorter period and with a lower intensity intervention than what is planned for this study. Since we are powered to detect small to medium effect-sizes magnitudes, we should be in a strong position even if effects are smaller on the global cognitive and functioning batteries.

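### The claim of over 80% power for any pattern with extreme arms d=.6 apart fails under 2:2:1 allocation: with control as an extreme arm, power can fall to 68%

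*Combined protocol and SAP*

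**What the plan says.** Power Considerations rests on 96 subjects with complete data, a within-subject correlation of .7 and two-sided alpha of .05. For the overall test it states: "Our design provides over 80% power to detect overall effects as small as" f=.13. It then describes this as "sufficient to detect any pattern of changes in the three study arms for which the difference between the two most extreme groups" reaches d=.6 when treatment ends. The sentence makes no exception for which arms are the extremes. A separate statement gives sufficient power for d=.5 between the two active arms.

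The arms are unequal by design. Randomization and Treatment Procedure says: "To optimize power for the primary comparison between the active treatments, we will use a 2:2:1 asymmetrical randomization procedure". After 20% attrition it projects "38 getting BFP training, 38 getting Cogpack training, and 19 getting the control intervention".

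Each specific aim names the control comparison as well as the active one; Aim 1 reads: "To compare the treatment effects of bottom-up training (BFP) to top-down training (Cogpack) as well as to a control condition on neurocognition". On the expected ordering, Background and Significance says: "We also expect that the bottom-up training will lead to superior effects on the primary and secondary outcomes relative to the top-down training".

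**The concern.** For a fixed distance between the extreme arms, Cohen's f depends on how many subjects sit in each arm and on where the middle arm lies. With 2:2:1 allocation, a pattern that sets the small control arm apart from two large active arms has less weighted variance than one that separates the two large arms. A single d=.6 therefore cannot correspond to a single minimum f without saying which arms are the extremes.

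At stake is how a null overall result is read. Anyone relying on the sentence would treat it as evidence against differences of d=.6 anywhere among the arms, although some of those patterns would be missed in up to 32% of trials. A null active-versus-control contrast has no stated detectable difference to be read against at all.

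**Working it through.** **Inputs.** Completers 38/38/19, so N=95 (Randomization and Treatment Procedure; the stated total of 96 is a rounding difference). r=.7 and two-sided alpha .05 (Power Considerations). Two time points with a group-by-time interaction (Analysis Plan By Specific Aim). With two time points this interaction is a one-way comparison of change, with variance 2(1−.7)=.6 in SD² units.

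**Formulas.** With allocation weights p = .4, .4, .2 and arm changes d_g:

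- V = Σ p_g(d_g − weighted mean)²
- f = √V / 2
- λ = N·f²·2/(1−r) = N·V/.6
- power from the noncentral F with 2 and N−3 = 92 df

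**Reproducing the plan's figures.** f=.13 gives λ = 95 × .0169 × 2/.3 = 10.70 and power 83% (also 83% at N=96). The exact f for 80% is .125. Active versus active at d=.5 with 38 per arm has noncentrality .5/√(.6 × 2/38) = 2.81 and power 79.5%. The convention is therefore the plan's own.

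**Extremes are the two active arms** (d, 0, control at x): V = .24d² + .16x² − .16dx. This is smallest at x = d/2. At d=.6, V = .072, f = .134, power 85%. With control level with either active arm, f = .147 and power 91%. The claim holds here.

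**Control is an extreme arm** (one active arm at d, the other at x, control 0): V = .24d² + .24x² − .32dx. This is smallest at x = 2d/3, where V = .1333d². At d=.6:

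| Active / other active / control | V | f | λ | Power |
|---|---|---|---|---|
| .6 / 0 / 0 | .0864 | .147 | 13.68 | 91% |
| .6 / .1 / 0 | .0696 | .132 | 11.02 | 84% |
| .6 / .15 / 0 | .0630 | .125 | 9.98 | 80% |
| .6 / .2 / 0 | .0576 | .120 | 9.12 | 76% |
| .6 / .3 / 0 | .0504 | .112 | 7.98 | 70% |
| .6 / .4 / 0 | .0480 | .110 | 7.60 | 68% (minimum) |
| .6 / .45 / 0 | .0486 | .110 | 7.70 | 68% |
| .6 / .5 / 0 | .0504 | .112 | 7.98 | 70% |
| .6 / .6 / 0 | .0576 | .120 | 9.12 | 76% |

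From .2 upward every row has f below .13, so power at f=.13 cannot cover those patterns. Power crosses 80% at x = .151, and (.6 − .151)/.6 = 75% of the possible positions of the middle arm lie beyond that point. Simulation of change scores (40,000 runs per pattern) agrees: .800 at .6/.15/0, .701 at .6/.3/0, .681 at .6/.4/0 and .760 at .6/.6/0.

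**Difference needed for every pattern.** At the worst position f = d√.1333/2 = .1826d. Setting this to .1254 gives d = .69.

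**Active versus control** (38 versus 19, SD of change √.6, 92 df): at d=.6 the noncentrality is .6/√(.6(1/38 + 1/19)) = 2.76 and power is 78%; at d=.5 power is 62%. Reaching 80% takes d = .62.

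**Sensitivity of the minimum power at d=.6:**

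- N=96 split exactly 2:2:1: 68.4%
- mixed model using all 120 baselines and 95 endpoints: 69.3% (80% in every pattern at d=.68)
- all 120 enrolled treated as completers: 78.8%
- 96 completers split equally: 78.5%
- baseline-adjusted variance 1−r², which is not the stated core model: 75.8% at N=96

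**The case against.** The strongest reply is that the overall test is not what the trial turns on. The primary hypotheses are the BFP-versus-Cogpack interactions, 2:2:1 was chosen openly to serve them, and their d=.5 figure holds to rounding. Nothing makes that contrast conditional on a significant overall test, and nothing says how a null overall result will be interpreted in a study that calls itself preliminary. This stands and limits the consequence.

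It can also be said that failure at d=.6 requires BFP and Cogpack to be less than about .45 apart, closer than the .5 the trial is sized to detect. At a .5 separation the overall test does well: 84% for .6/.1/0, 90% for .7/.2/0 and 98% for .95/.45/0. That is correct. However, the expectation that BFP beats Cogpack carries no size of its own, and the sentence at issue covers all patterns, including the one where both trainings beat control equally.

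The .6/.45/0 case is only an illustration. The .45 is the plan's cited figure for cognitive training in general and is not assigned to Cogpack. Likewise, the 75% share describes positions of the middle arm and is not a probability of failure.

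The shortfall depends on r: at r=.78 the minimum would be 82%. But the plan assumes .7, and at that value no completer-based reading under the stated model makes the sentence true.

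The missing active-versus-control figure is an omission rather than an error, and the main point does not depend on it.

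**Conclusion.** The concern holds: the sentence is wrong as written. At d=.6 the overall test has 85% to 91% power when the two active arms are the extremes. When control is an extreme it has 68% to 91%, and it is below 80% once the other active arm is more than about .15 SD from control. With that arm .2 to .6 above control, 24% to 32% of trials would miss the effect. Covering every pattern needs d of about .69 (.68 if all baselines enter the mixed model). Active versus control would be missed in 22% of trials at d=.6 and 38% at d=.5. These figures rest on 38/38/19 completers, r=.7, two-sided alpha .05 and the 2-df group-by-time test. The f=.13 figure stands, and so, to rounding, does the d=.5 active comparison.

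**What to change.** In Power Considerations, replace the clause covering every pattern with a statement along these lines: power exceeds 80% for d=.6 between the two active arms with control anywhere between them; when control is an extreme arm, power at d=.6 ranges from 68% to 91% depending on the other active arm, and exceeds 80% only if that arm is within about .15 SD of control; 80% power in every pattern requires d of about .69.

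Add one sentence giving the detectable active-versus-control difference: about d=.62 for 80% power, with 78% at d=.6 and 62% at d=.5. State that the figures are completer-based and assume r=.7.

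The cost is one reworded sentence and one new one. No patients are added and no analysis changes; the stated power simply becomes less favourable for patterns in which control is an extreme arm.

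### The closing claim of power for small-to-medium effects fits only within-group change; for between-arm contrasts 80% power needs d of about .50 (BFP–Cogpack) and .62 (either active arm against games)

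*Combined protocol and SAP*

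**What the plan says.** All of the power statements are in Power Considerations. The calculations "assume a two-sided significance level of $\alpha=.05" and, on correlation, "We also assume a within-subject autocorrelation of $r = .7".

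The section then makes three kinds of statement:

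- **Overall test of the three arms.** "Our design provides over 80% power to detect overall effects as small as $f=.13". The plan treats this as enough for any arrangement of the arms in which the two furthest apart differ by d=.6 at endpoint.
- **BFP against Cogpack, group by time.** Sufficient power for d=.5 at endpoint. This is named as the comparison of primary interest.
- **Change within an arm.** Over 80% power for d=.35 (active arms) and d=.5 (control). Only here are effects called small to medium by Cohen's conventions.

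After a paragraph on pilot changes in Cogpack training tasks (d=.5 to 2.5), the section ends: "Since we are powered to detect small to medium effect-sizes magnitudes, we should be in a strong position even if effects are smaller". The sentence goes on to name the global cognitive and functioning batteries.

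Aim 1 in Analysis Plan By Specific Aim reads "To compare the treatment effects of bottom-up training (BFP) to top-down training (Cogpack) as well as to a control condition on neurocognition". Aims 2 and 3 have the same form for MMN and functional capacity. No pairwise detectable effect against control is given anywhere.

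Background and Significance cites meta-analyses in which "cognitive training has a moderate effect-size impact on cognitive functioning (0.45) and a lower impact on daily functioning (0.36").

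**The concern.** The section says that its primary hypotheses all concern comparisons among the arms, yet its conclusion borrows a label attached to within-arm change. Within-arm change is easier to detect, because it carries the sampling error of one mean change and not two. A reader who takes the last sentence at face value will believe that the between-arm contrasts can pick up effects well below d=.5.

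Two things are at stake. The reader cannot learn from the plan how weak the active-versus-games contrasts are, although they are part of all three aims. The one between-arm statement that seems to cover games, the d=.6 claim for the overall test, is presented as holding for every pattern. With a games arm half the size of the others, it may not.

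**Working it through.** **Inputs.** Two-sided alpha .05 and r=.7 (Power Considerations). Allocation is "2:2:1 asymmetrical randomization procedure resulting in a total of 48 subjects in the BFP group", with 48 in Cogpack and 24 in control. After 20% attrition, completers are 38, 38 and 19 (Randomization and Treatment Procedure). These sum to 95, and the plan rounds to 96. Error df = 95 − 3 = 92. The power target is 80%. For BFP–Cogpack the plan says only that power is sufficient, so 80% is taken from the neighbouring sentences.

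**Standard errors.** In units of the outcome SD:

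- SD of change = sqrt(2(1 − .7)) = sqrt(.6) = .775
- SE of a difference in change = .775 × sqrt(1/n1 + 1/n2)
- BFP–Cogpack: .775 × sqrt(1/38 + 1/38) = .178
- Active–games: .775 × sqrt(1/38 + 1/19) = .218

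**Reproducing the plan's figures.**

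- BFP–Cogpack: noncentral t gives 80% power at d=.503. The stated d=.5 is right.
- Overall test: noncentrality λ = f² × N × 2/(1 − r) = .0169 × 95 × 2/.3 = 10.7, power 83%. The stated f=.13 is right.
- Within-arm: about 80% for both figures by the normal approximation (77% and 76% by paired t).

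**Active arm against games, not stated in the plan.** 80% power at d=.616, or about .62.

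| True d | BFP–Cogpack power | Active–games power |
|---|---|---|
| .20 | 20% | 15% |
| .36 | 52% | 37% |
| .45 | 71% | 53% |

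The rows at .36 and .45 are the cited training effects. They serve as a benchmark only for the active–games column.

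**The d=.6 claim for the overall test.** λ = Σ n(m − weighted mean)² / .6, with 2 and 92 df. Equivalent f = sqrt(λ × .3/190).

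| Endpoint differences (BFP, Cogpack, games) | Sum of squares | λ | f | Power |
|---|---|---|---|---|
| .6, 0, .3 (active arms extreme) | 6.84 | 11.4 | .134 | 85% |
| .6, 0, 0 (Cogpack ties with games) | 8.21 | 13.7 | .147 | 91% |
| .6, .3, 0 (games extreme, Cogpack midway) | 4.79 | 7.98 | .112 | 70% |
| .6, .6, 0 (games extreme, active arms equal) | 5.47 | 9.12 | .120 | 76% |

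So f=.13 matches d=.6 when the two large arms are the extremes. It does not when the half-size games arm stands alone at one end. 80% power needs λ of about 9.96. The last two rows reach that at .6 × sqrt(9.96/9.12) = .63 (active arms equal) and .6 × sqrt(9.96/7.98) = .67 (midway). The least favourable pattern puts the other active arm two-thirds of the way up: sum of squares 12.67 × .36 = 4.56, λ = 7.6, power 68%, and .6 × sqrt(9.96/7.6) = .69 for 80%.

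**Sensitivity of the 80% detectable effects.**

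| Assumption | BFP–Cogpack | Active–games |
|---|---|---|
| r=.6 | .58 | .71 |
| r=.7 (plan) | .50 | .62 |
| r=.8 | .41 | .50 |
| r=.7, baseline-adjusted, SD sqrt(1 − .49) = .714 | .46 | .57 |
| r=.7, no dropout (48/48/24) | .45 | .55 |

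**The case against.** The strongest reply is that no pairwise figure printed in the plan is wrong. The d=.5 for BFP–Cogpack is disclosed and reproduces, and it sits at the top of a small-to-medium range. This stands. The fault lies in the summary label, the missing figure against games, and the reach of the d=.6 claim.

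It can also be said that the word smaller in the closing sentence means smaller than the pilot task changes, not smaller than .45 or .36. That is the right reading in context. The sentence still rests on the small-to-medium premise, which the between-arm contrasts do not meet.

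Weaker power against games is partly a declared trade-off: the 2:2:1 allocation was chosen to favour the active–active comparison, and the Statistical Plan calls the study preliminary. Completer numbers are also conservative, since loss is put at up to 20% and those who stop treatment are asked back for a final assessment. Even with no loss, however, the active–games figure is .55. A declared trade-off is a reason to print its size.

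A reader might go further and infer three things that the documents do not support:

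- **That BFP–Cogpack is underpowered against .45 and .36.** Those are effects of cognitive training, not of one training over another. The documents give no expected BFP–Cogpack difference.
- **That a non-significant result against games is likely.** At .45, power is 53%, so significance is slightly more likely than not. Only at .36 does the balance tip.
- **That a null will be read as equivalence.** Background and Significance promises that "this study will provide a clinically meaningful answer, even if our hypothesis is incorrect", but this also covers Cogpack proving superior, which a two-sided test can show. No passage says that a null would be taken as no difference. An equivalence margin would be a preference, and with 95% confidence half-widths of about .35 SD (BFP–Cogpack) and .43 SD (active–games) it could rarely be met.

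**Conclusion.** The concern holds as a misstatement of what the design can detect between arms. The small-to-medium label belongs to within-arm change. Between arms, 80% power needs d of about .50 for BFP–Cogpack and .62 for either active arm against games, and the second figure is absent although three aims call for it. The claim of over 80% power for every pattern at d=.6 is incorrect when games alone is an extreme: about 70% with the other active arm midway and 76% with both active arms equal. It does hold when BFP and Cogpack are the extremes, or when one active arm ties with games.

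The figures rest on r=.7, the projected completers and a change-score analysis. The 53% and 37% rest on two further assumptions: that the cited training effects apply to training against games, and that the daily-functioning effect carries over to the UPSA, a functional-capacity measure. The documents give no comparable benchmark for MMN. The d=.5 for BFP–Cogpack and the f=.13 for the overall test stand as printed.

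**What to change.** In Power Considerations:

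1. Confine the small-to-medium description to within-group change.
2. Restrict the d=.6 statement to patterns in which BFP and Cogpack are the extreme arms, or restate it. With games alone at one extreme, give about 70% (other active arm midway) and 76% (active arms equal). If a single figure for every pattern is wanted, it is about d=.69.
3. Replace the closing sentence with text such as: With 38/38/19 completers, r=.7 and two-sided alpha .05, the design has 80% power for a between-arm difference of d=.50 for BFP against Cogpack and d=.62 for either active arm against control; these become .41 and .50 at r=.8, and .58 and .71 at r=.6.
4. Optionally, add that power against control would be about 53% at d=.45 and 37% at d=.36, with the two assumptions stated.

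The cost is wording only: no more patients, and no change to the allocation or the analysis. The downside is that the stated power becomes less favourable.
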